## Participants

Twenty-one healthy participants (12 males, 9 females, age  $26.8 \pm 5.57$  years, body height  $172.8 \pm 7.58$  cm, body weight  $65.9 \pm 8.53$  kg) were recruited for this study. Exclusion criteria included relevant musculoskeletal injuries, abnormal gait deviations, and weight bearing restrictions. Prior to the experiment, participants had their footedness evaluated to ensure that they were right footed. The University of Texas Institutional Review Board approved the experimental protocol and subjects were provided informed written consent.

## Experimental setup and protocol

Participants were tasked with traversing a treadmill while bearing scuba weights secured with a diving belt (Scuba Choice, Los Angeles CA). Weights of 4 kg, 6 kg, and 8 kg were suspended on the pelvis in three configurations: weight evenly distributed between both anterior iliac crests (Bilateral, BI), weight on the 4th lumbar vertebrae (Lumbar, L), and weight on the non-dominant left anterior iliac crest (Unilateral, UNI). [Fig. 1](#) illustrates these placements.

We collected Motion capture marker data with a 13-camera motion capture system and 36 active markers attached to the lower body and torso segment (Phase Space, San Leandro, CA). Ground reaction forces (GRF) were measured through force plates in an instrumented split-belt treadmill (Bertec, Columbus, OH). Surface electromyography data (EMG) (Bortec, Calgary, AL) were collected from the rectus femoris (RF), medial hamstring (MH), tibialis anterior (TA), and lateral gastrocnemius (GAS) of each leg.

[figure not shown]

Fig. 1. Weight placements during an experiment. Also shown are the motion capture LEDs, EMG electrodes, and split belt treadmill.

Participants walked for 1m30s at a speed of 1.1 m/s for every combination of weight (4, 6 and 8 kg), placement (BI, UNI, L), and no weight (NW) in pseudo-randomized order. The participants were exposed to each condition two times, for 20 total trials. After every five trials subjects were given a break of 2 min.

#### Data processing

Using GRFs, we defined heel strike and toe off events, which were then used to identify gait phases. Starting from heel strike, the gait phases were defined as initial stance, mid stance, late stance, and swing, ending the gait cycle with the proceeding heel strike. For each trial, we

ignored the first 30 s to account for familiarization to the condition. For outlier detection, we removed an individual stride if the waveform exceeded 2 inter-quartile-ranges from the median waveform for more than 40% of the gait cycle. The mean waveform from the last 30 strides was evaluated.

We recorded all biometric data at 960 Hz. First, all these signals were downsampled to 480 Hz. Force plate data were low-pass filtered with 4th order Butterworth filter at 20 Hz. Motion capture data were low-pass filtered with 4th order Butterworth filter at 6 Hz. Surface EMG signals were processed with a high-pass filter of 40 Hz, demeaned, rectified, and low-pass filtered at 4 Hz. We used motion capture data and GRFs with an open-source musculoskeletal simulation software, OpenSim 4.3. We scaled a musculoskeletal model to match the anthropometry of each subject, and then performed inverse kinematics and dynamics for joint angles and moments, respectively.

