#### Outcome measures

We contextualized the joint motion for the hips and knees as Range-of-Motion (ROM), the difference between the maximum and minimum joint angles within a given period. We analyzed the effect of weight on the hip and knee sagittal plane motion during initial stance phase. We quantified pelvic tilt and obliquity as the average position within a gait phase.

EMG signals were normalized via the mean-dynamic method centering the EMG signal around 1. For data analysis, the EMG signal was integrated along each gait phase to calculate the integrated EMG (iEMG) values. We analyzed the RF muscle activation during initial stance and the GAS muscle activation during late stance.

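### Hip and knee ROM appears to be read from the 30-stride mean waveform; this can understate ROM, mainly at the knee, and would bias load contrasts if stride timing variability differs by condition

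*Combined protocol and SAP*

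**What the plan says.** Two sections of the combined protocol and SAP bear on this.

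- **Data processing** sets the unit of analysis: "The mean waveform from the last 30 strides was evaluated". Strides run from heel strike to heel strike: "Using GRFs, we defined heel strike and toe off events, which were then used to identify gait phases".
- **Outcome measures** defines hip and knee motion as "Range-of-Motion (ROM), the difference between the maximum and minimum joint angles within a given period" and sets the period: "We analyzed the effect of weight on the hip and knee sagittal plane motion during initial stance phase". Pelvic tilt and obliquity are instead averages within a gait phase.

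Taken together, the strides are averaged and the maximum minus minimum is then read from the average. The order is not stated outright, but no section describes a per-stride ROM. The limits of initial stance are not given as percentages of the cycle.

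**The concern.** Averaging first makes no difference to an outcome that is itself an average over a common window, such as pelvic tilt or obliquity. A maximum minus a minimum behaves differently. If the knee reaches peak flexion slightly earlier in some strides and later in others, the averaged curve has a lower, flatter peak than the strides that went into it. Its range is then too small as a summary of what the joint did in each stride.

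A constant loss would cancel in comparisons between conditions. A loss that varies with condition would not. The subject random effect in the Statistical analysis section removes offsets that belong to a person, but not offsets that move with the weight or its placement. If some loads made stride timing less regular, they would show a smaller knee ROM even with unchanged excursion in every stride. A true increase could then be partly hidden, or a small decrease could appear.

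**Working it through.** **No plan figure to reproduce.** The document gives no ROM values, standard deviations, expected differences, limits of initial stance or stride timing variability by condition. Direction can be proved; size can only be illustrated.

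**Direction.** Let x_i(t) be the joint angle in stride i, over a window common to all strides. At every t, the mean of x_i(t) is at most the mean of the stride maxima, so max(mean) ≤ mean(max). In the same way, min(mean) ≥ mean(min). Subtracting gives

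ROM of the mean waveform ≤ mean of the stride ROMs.

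Equality holds when all strides reach their maximum at one shared time and their minimum at another.

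**Inputs.**

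- From the document: 30 strides per trial, cycles starting at heel strike, ROM as maximum minus minimum in initial stance.
- Assumed: knee excursion A = 13 degrees; peak at T = 14% of the cycle on average; stride-to-stride SD of peak time σ = 1% in one condition and 2% in the other; window ending at 12%, 15% or 20%.
- Assumed curve: every stride starts from the same point at heel strike and rises as (A/2)(1 − cos(πt/T)). After the peak it falls back either slowly (to its heel-strike angle at 40% of the cycle) or symmetrically (at twice its own peak time, 28% on average).

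**Approximation by hand, symmetric curve, peak inside the window.** Near its peak the curve is A − ½c(t − T)², with

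c = (A/2)(π/T)² = 6.5 × (3.1416/14)² = 6.5 × 0.0504 = 0.327.

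Averaging over strides lowers the peak by about ½cσ²:

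- σ = 1%: ½ × 0.327 × 1 = 0.16 degrees
- σ = 2%: ½ × 0.327 × 4 = 0.65 degrees
- difference: 0.65 − 0.16 = 0.49 degrees

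On the slow-return curve the curvature after the peak is only 6.5 × (3.1416/26)² = 0.095, so the loss is smaller.

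**Simulation of the same set-up** (30 strides per trial, heel strike fixed). Entries are mean stride ROM minus ROM of the mean waveform, in degrees.

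| Curve | Window ends | σ = 1% | σ = 2% | Spurious contrast |
|---|---|---|---|---|
| Slow return | 12% | 0.00 | 0.01 | 0.01 |
| Slow return | 15% | 0.06 | 0.15 | 0.09 |
| Slow return | 20% | 0.07 | 0.23 | 0.16 |
| Symmetric | 12% | 0.00 | 0.09 | 0.09 |
| Symmetric | 15% | 0.15 | 0.57 | 0.42 |
| Symmetric | 20% | 0.16 | 0.64 | 0.48 |

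The spurious contrast is therefore about 0.1 to 0.5 degrees when the window contains the peak, and 0.01 to 0.1 degrees when it ends at 12%. The loss grows with timing SD, so a larger rise would give more. With equal σ and the same curve shape in both conditions, the contrast bias is about zero.

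**Hip.** With an assumed cosine of 40 degrees total excursion, extending steadily through early stance, and a 20% window, the shortfall is 0.02 degrees at σ = 1% and 0.08 at σ = 2%. The contrast is 0.08 − 0.02 = 0.06 degrees. That model shifts the whole curve and does not hold heel strike fixed.

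**The case against.** **The order of operations is inferred.** True. Outcome measures does not say that ROM was read from the mean waveform. It is the natural reading, and if ROM was computed per stride, the text should say so.

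**Bias in load contrasts is not shown.** This stands in full. A reader might infer that heavier or one-sided loads make timing less regular, so that the reported contrasts are biased. The document contains no timing variability by condition. Participants were healthy and walked at a fixed speed, and the analysis "ignored the first 30 s to account for familiarization to the condition". These features plausibly limit the effect.

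**Stride screening already deals with it.** Only in part. The rule is that "we removed an individual stride if the waveform exceeded 2 inter-quartile-ranges from the median waveform for more than 40% of the gait cycle". A modest shift around one early-stance peak affects too little of the cycle to trigger that.

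**Larger figures are possible.** Shifting entire knee curves in time, with the same excursion and peak, gives shortfalls of 0.22 and 0.78 degrees at σ = 1% and 2% for a 0–15% window, and 0.08 and 0.34 for 0–12%. A reader might infer contrasts of 0.78 − 0.22 = 0.56 and 0.34 − 0.08 = 0.26 degrees, and so a material bias even where the window stops before the peak. That model also moves the heel-strike minimum, which does not fit strides that all start at heel strike.

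**Per-stride ROM has its own faults.** Noise pushes a single-stride range upward, so the two summaries are partly different quantities. But "Motion capture data were low-pass filtered with 4th order Butterworth filter at 6 Hz", and at an assumed noise SD of 0.2 to 0.5 degrees after that filter the inflation is only about 0.03 degrees or less. Mean per-stride ROM also moves with timing when the window cuts near the peak: for a 0–12% window it falls from 12.29 to 11.84 degrees as σ rises from 1% to 3%. That is a real change in excursion within the window, not an artefact of averaging.

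**Conclusion.** The point holds in a conditional form. On the natural reading, ROM is taken from an averaged curve, and the direction of the resulting error is certain: it can lower ROM relative to the mean per-stride value and cannot raise it. The practical issue is the knee, and only if initial stance includes the flexion peak.

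The document does not support saying that ROM is understated at both joints in every condition. There is no loss where the extremes fall at times shared by all strides, such as the window edges, which is plausible for the hip. Nor does it support saying that the load contrasts are biased. That needs timing variability to differ between conditions, which is an open question.

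The sizes above rest wholly on the assumed excursion, peak time, curve shape, window and rise in timing SD. On a 13-degree excursion, 0.1 to 0.5 degrees is roughly 1% to 4%. No figure in the document shows whether that would alter a conclusion. The change is worth making because it costs little and removes a loss whose size a reader cannot check.

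**What to change.** Compute hip and knee ROM within initial stance for each retained stride, using that stride's own GRF events. Average the 30 values to give the trial value that enters the mixed model. Keep the mean waveform for plots and for the averaged pelvic outcomes.

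Alongside this, state the order of operations and the limits of initial stance, and report stride-to-stride variability in peak timing for each condition. Readers can then see whether the two summaries could differ between loads. If the mean-waveform ROM is kept as the main measure, the per-stride version should at least be shown as a sensitivity analysis.

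The cost is a short change to the processing code and a rerun on data already held; nothing new has to be collected. The downside is slightly more exposure to single-stride noise, which the 6 Hz filter and the stride screening already limit.

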#### Outcome measures

We contextualized the joint motion for the hips and knees as Range-of-Motion (ROM), the difference between the maximum and minimum joint angles within a given period. We analyzed the effect of weight on the hip and knee sagittal plane motion during initial stance phase. We quantified pelvic tilt and obliquity as the average position within a gait phase.

EMG signals were normalized via the mean-dynamic method centering the EMG signal around 1. For data analysis, the EMG signal was integrated along each gait phase to calculate the integrated EMG (iEMG) values. We analyzed the RF muscle activation during initial stance and the GAS muscle activation during late stance.

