## Statistical analysis

R 4.1.1 (2021 The R Foundation for Statistical Computing) was used for statistical analysis. One subject was removed from the dataset due to technical errors with recording the data.

We used a linear mixed regression model (*lme4* 1.1.27.1 and *lmerTest* 3.1.3) with two fixed effects (weight and placement) along with a no weight condition and one random effect (subject) and  $\alpha < 0.05$ . A Tukey Honestly Significant Difference post-hoc test was performed to determine pairwise differences between weights, placements, and their interactive effects.

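### Does the unnamed divisor in the EMG normalisation undermine the iEMG comparisons between load conditions?

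*Combined protocol and SAP*

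**What the plan says.** The EMG outcome is built in three steps in the combined protocol and SAP.

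- **Data processing:** "Surface EMG signals were processed with a high-pass filter of 40 Hz, demeaned, rectified, and low-pass filtered at 4 Hz". On the unit carried forward, the section says "The mean waveform from the last 30 strides was evaluated".
- **Outcome measures, scaling:** "EMG signals were normalized via the mean-dynamic method centering the EMG signal around 1".
- **Outcome measures, summary:** "the EMG signal was integrated along each gait phase to calculate the integrated EMG (iEMG) values". Two muscle-phase pairs are then named: "We analyzed the RF muscle activation during initial stance and the GAS muscle activation during late stance".

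Under Experimental setup and protocol, subjects walk under "every combination of weight (4, 6 and 8 kg), placement (BI, UNI, L), and no weight (NW) in pseudo-randomized order", and "The participants were exposed to each condition two times, for 20 total trials". Under Statistical analysis, these conditions enter a linear mixed model "with two fixed effects (weight and placement) along with a no weight condition", with subject as the only random effect.

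No section says which data supply the mean used for scaling, and no maximal contraction or separate reference trial is described.

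**The concern.** The choice of divisor decides what iEMG measures. With one fixed divisor per subject, muscle and leg, phase iEMG is a level of activity, and a contrast between load and no load shows how far that level moved. If each trial or condition is divided by its own mean, every normalised cycle averages 1 by construction. Phase iEMG then becomes the share of the cycle's activity that falls in that phase.

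The design makes this worth asking. The load is carried through the whole gait cycle at a fixed speed, so a broad rise in activity is conceivable, and own-mean division would hide exactly that. A rise elsewhere in the cycle would also pull down the analysed phase. A null result for the rectus femoris or gastrocnemius could not then be read as no change in activation.

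**Working it through.** The plan gives no effect size, phase share or power figure for EMG, so there is no stated figure to reproduce. The check is algebra on assumed values.

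**Inputs from the document.** Three weights by three placements plus no weight give 3 × 3 + 1 = 10 conditions. Two exposures each give 20 trials per subject, as stated: 18 loaded and 2 unloaded. Loads run from 4 to 8 kg and mean body weight is 65.9 kg.

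**Assumed.** *s* is the analysed phase's share of no-weight cycle activity, *g* the load multiplier inside that phase, and *r* the multiplier in the rest of the cycle.

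**1. Ratio of loaded to no-weight phase iEMG**

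- Fixed divisor: *g*
- Own-trial or own-condition mean: *g* / (*s·g* + (1 − *s*)·*r*)

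**2. Results under own-mean division**

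- Uniform rise, *g* = *r* = 1.20: 1.20 / 1.20 = 1.00 for every *s*. The effect cancels.
- Rise of 20% in the analysed phase only (*r* = 1), with *s* = 0.1, 0.3, 0.6: 1.20/1.02, 1.20/1.06 and 1.20/1.12, or +17.6%, +13.2% and +7.1%. The sign is kept and the size shrinks.
- Rise of 20% in one other phase holding 0.1, 0.3 or 0.6 of cycle activity: 1/1.02, 1/1.06 and 1/1.12, or −2.0%, −5.7% and −10.7%, where the truth is 0%.
- Rise of 10% in the analysed phase and 20% elsewhere: 1.10/1.18 = 0.932 at *s* = 0.2 and 1.10/1.14 = 0.965 at *s* = 0.6. The sign reverses.

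**3. Effects scaled to the load.** The loads are 4/65.9 = 6% to 8/65.9 = 12% of mean body weight. Suppose activity rose in proportion, which is a further assumption. At a share of 0.3, a rise in the analysed phase only would read as 1.06/1.018 = +4.1% or 1.12/1.036 = +8.1%. A rise only in another phase with that share would read as 1/1.018 = −1.8% or 1/1.036 = −3.5%.

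**4. Results under a fixed divisor.** Take a uniform 20% rise in all 18 loaded trials and a divisor pooled over 20 trials: (2 × 1 + 18 × 1.2)/20 = 1.18. No weight reads 1/1.18 = 0.847 and loaded reads 1.2/1.18 = 1.017. The ratio is still 1.20, and pooled over the 20 trials the signal averages 1.

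**5. Which reading does the text support?** Step 4 shows that a pooled divisor centres the signal around 1 just as an own-mean divisor does, so that phrase does not separate the two. In Data processing, the per-trial wording attaches only to dropping the first 30 s. The filtering sentence names no unit, and its demeaning step comes before rectification, so it removes an offset and sets no scale. The sentence on the last 30 strides says what was evaluated, not what it was divided by.

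**The case for a change.** The strongest case for acting is that the gap is real and sits at a step that both EMG outcomes must pass through. The sentence is complete, nothing has been blacked out, and a reader cannot tell whether the contrasts concern level or distribution. Under own-mean division the distortion can reverse a sign. Checking is cheap, because all 20 trials per subject are recorded and a changed divisor needs only a re-run.

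The gap and the algebra stand. The step from them to a defect does not. The harm requires own-mean division, which the document neither states nor favours, and under a common divisor there is nothing to correct.

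Nor is own-mean iEMG invalid in itself. It describes how activity is distributed over the cycle, which is a legitimate quantity for phase-specific outcomes if it is labelled as such.

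Prescribing one fixed reference would bring its own trade-off. In step 4 the contrast in the linear model is 0.2/1.18 = 0.169 with the pooled divisor, against 0.20 in no-weight units, because 18 of the 20 trials that set the pooled unit are loaded. The no-weight alternative rests on two trials. At an assumed between-trial coefficient of variation of 10% and independent trials, its standard error is 10/√2 = 7.1%, against 10/√20 = 2.2% for the pooled mean. That error is shared by all of a subject's conditions, so it cancels from within-subject ratios. The document gives no ground for ranking the two references.

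**Conclusion.** The concern does not call for a change. The plan leaves the EMG divisor unnamed, but this is a missing detail rather than a demonstrated fault. An analyst comparing conditions within a subject can sensibly use one divisor per subject, muscle and leg, and the wording allows it. On that reading the ratio of loaded to no-weight iEMG is undistorted.

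On the other reading, a uniform effect would be lost entirely and other effects shifted by the amounts in step 2. Those amounts depend on effects and phase shares that the document does not give, so the true size of any distortion cannot be found from it.

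The reach is limited: rectus femoris in initial stance and gastrocnemius in late stance. Hip and knee range of motion, pelvic tilt and pelvic obliquity do not use this step, and no section names EMG as a primary outcome. Evidence that own-trial or own-condition means were in fact used would change this conclusion; the document contains none.

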## Statistical analysis

R 4.1.1 (2021 The R Foundation for Statistical Computing) was used for statistical analysis. One subject was removed from the dataset due to technical errors with recording the data.

We used a linear mixed regression model (*lme4* 1.1.27.1 and *lmerTest* 3.1.3) with two fixed effects (weight and placement) along with a no weight condition and one random effect (subject) and  $\alpha < 0.05$ . A Tukey Honestly Significant Difference post-hoc test was performed to determine pairwise differences between weights, placements, and their interactive effects.

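### The plan names only Tukey pairwise comparisons for the weight-by-placement interaction, and no pair of loaded conditions tests an interaction

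*Combined protocol and SAP*

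**What the plan says.** Under Experimental setup and protocol, participants walked "for every combination of weight (4, 6 and 8 kg), placement (BI, UNI, L), and no weight (NW) in pseudo-randomized order". The replication is also given: "The participants were exposed to each condition two times, for 20 total trials".

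The Statistical analysis section describes a linear mixed model "with two fixed effects (weight and placement) along with a no weight condition and one random effect (subject"), fitted with lme4 and lmerTest at a 0.05 level. The interaction is mentioned once, in the sentence on post-hoc testing: "A Tukey Honestly Significant Difference post-hoc test was performed to determine pairwise differences between weights, placements, and their interactive effects".

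The section gives no model formula and lists no weight-by-placement term. It describes no F or likelihood-ratio test of any term, and it defines no contrast for the interaction.

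**The concern.** Three weights crossed with three placements invite the question whether the effect of placement changes with load, and the section itself announces interactive effects. That question concerns a difference between differences, for example UNI minus BI at 8 kg compared with UNI minus BI at 4 kg. A comparison of two cell means does not answer it.

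If interaction is judged by noting that a placement difference is significant at one weight and not at another, an effect that is identical at all three weights can look weight-dependent. This happens because chance carries it over the Tukey threshold in one place and not in another. A statement about interactive effects could then describe main effects plus noise. The comparisons between weights and between placements as such are not affected.

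**Working it through.** **Inputs from the documents.** There are 3 weights, 3 placements, one unloaded condition and 2 exposures per condition (Experimental setup and protocol). Participants gives "Twenty-one healthy participants", and Statistical analysis removes one, so 21 - 1 = 20 are analysed.

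**The plan's own figure.** (3 x 3 + 1) x 2 = 20 trials, which agrees with the stated total. The layout is nine loaded cells plus NW.

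**Contrast algebra (no assumed effects needed).** Nine loaded cells give 9 x 8 / 2 = 36 pairs, or 10 x 9 / 2 = 45 with NW. The documents state neither count. A contrast tests interaction only if it lies wholly in the (3 - 1) x (3 - 1) = 4-df interaction space. Each pairwise contrast has squared length 2, which splits as follows:

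| Type of pair | Number | Weight | Placement | Interaction |
|---|---|---|---|---|
| Same weight, different placement | 9 | 0 | 0.667 | 1.333 |
| Same placement, different weight | 9 | 0.667 | 0 | 1.333 |
| Different on both | 18 | 0.667 | 0.667 | 0.667 |

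Every row has a main-effect component, so 0 of 36 pairs is an interaction contrast. The nine further pairs with NW are also single differences of two cell means, so they do not help. The elementary interaction contrasts use four cells each, and there are 3 weight pairs x 3 placement pairs = 9 of them.

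**Illustration of the consequence (assumed effects).** The assumptions are:
- the interaction term is in the model;
- data are complete for 20 subjects;
- residuals are independent given a subject intercept, which cancels from within-subject differences;
- there is no true interaction, so UNI exceeds BI by the same amount at 4, 6 and 8 kg.

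The quantities that follow are:
- Variance of a cell mean: 1/(20 x 2) = 1/40 of the residual variance.
- SE of a cell difference: sqrt(2/40) = 0.22 residual SD.
- Residual df: 400 - 20 - 9 = 371.
- Tukey threshold: 3.12 SE for a nine-cell family, or 2.35 SE if Tukey is applied to the three placements within each weight.

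The three UNI-BI differences use separate cells. If each is significant with probability p, the chance that one or two are significant but not all three is 1 - p^3 - (1 - p)^3. At a true difference of 3 SE with the nine-cell threshold, p is about 0.45, which gives 1 - 0.09 - 0.17 = 0.74. Simulation with 200,000 data sets per effect size gives:

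| True UNI-BI difference (SE) | 0 | 1 | 2 | 3 | 4 | 5 | 6 |
|---|---|---|---|---|---|---|---|
| Mixed pattern, nine-cell family | 0.6% | 5% | 34% | 74% | 46% | 9% | 0.6% |
| Mixed pattern, within each weight | 6% | 25% | 69% | 57% | 14% | 1% | 0% |

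The 4-df interaction F test rejects in about 5% of data sets at every effect size. If a significant F test is required first, the mixed UNI-BI pattern falls to at most about 4.6%. Averaging the two exposures (200 - 20 - 9 = 171 df, threshold 3.14) barely changes the nine-cell row: 5%, 34%, 74%, 48% and 10% at 1 to 5 SE.

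**The case against.** The strongest reply is that this is brevity and not a wrong analysis. The section is a short account of methods. lmerTest can test model terms, the word post-hoc ordinarily implies a preceding test, and Tukey-adjusted cell comparisons are a normal follow-up to a factorial model. The phrase on interactive effects could even mean Tukey-adjusted double differences. This stands in part: the text does not show that pairwise tests replaced an interaction test. A reader might infer that no interaction was ever tested, and the documents do not support that. But naming a package does not specify a test, no double difference is defined, and nothing makes an interaction claim depend on an overall test.

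A second reply concerns the percentages, and it largely stands. The formula reaches 75% for any three independent tests with p = 0.5, so the 74% mainly reflects an assumed effect placed near the threshold. No section states that weight-dependence is judged from patterns of significance, and the documents report no results. The figures also require a fitted interaction. Under a literally additive model, the fitted UNI-BI difference and its SE are the same at all three weights, so a mixed pattern cannot arise within one Tukey family. In that case the defect is a different one: no interaction is estimated.

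A third reply is that the full set of nine double differences exceeds what is needed. That is fair where no specific interaction is claimed, since one F test answers the overall question.

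**Conclusion.** The point holds. The only procedure that the plan ties to interactive effects cannot isolate an interaction: 0 of 36 loaded-cell pairs is an interaction contrast. That result follows from the 3x3 layout alone. Under either reading of the model, the section states no valid basis for an interaction claim. With an interaction term, the named comparisons mix it with main effects. Without one, there is nothing to test.

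The harm is conditional. It arises only if weight-dependence is inferred from which pairs are significant, and then mainly for moderate effects. The range from under 1% to about 74% rests on assumed effect sizes, a fitted interaction term, independent residuals and complete data from 20 subjects. It should not be read as the probability that this study reports a false interaction. Nor do the documents show that any reported interaction is spurious.

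**What to change.** State the model formula: an NW indicator, weight, placement and their 3x3 interaction, with a random subject effect. For each outcome, report the 4-df interaction F test and base any interaction claim on it. Where it is significant and a particular dependence on weight is claimed, test that with difference-in-differences contrasts adjusted for multiplicity (nine if the full elementary set is used). Keep the Tukey cell pairs, but describe them as comparisons between conditions and not as interactive effects.

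No new data are needed. If the interaction is already in the model, the F test and contrasts come from the existing fit. If it is not, a refit is needed and uses 4 more df (400 - 20 - 5 = 375 becomes 371 under the assumptions above). The real cost is precision: a difference-in-differences has SE sqrt(4/40) = 0.32 residual SD against 0.22 for a cell pair, a factor of sqrt(2) = 1.41, so fewer interactions may be claimed.
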